1 PROTOCOL SUMMARY

1.1 SYNOPSIS

Title:	Feasibility of a meal delivery intervention for postpartum weight management
Study Description:	This is a single-group pilot study to assess the feasibility and acceptability of a meal delivery intervention among low-income postpartum women with obesity.
Objectives:	The objectives of the study are to assess the feasibility and acceptability of a meal delivery intervention among low-income postpartum mothers with obesity.
Endpoints:	The primary endpoint is participant adherence to the 8-week study intervention.
Study Population:	Participants will be 11 mothers who are 5-45 weeks postpartum, have obesity, and qualify for Medicaid or the Special Supplemental Nutrition Program for Women, Infants, and Children (i.e., have a household income at or below 185 percent of the federal poverty line).
Phase:	N/A
Description of Study Intervention:	An 8-week meal delivery intervention consisting of 10 home-delivered meals per week provided by a local meal delivery company supplemented by remote weekly behavioral support with study staff to help low-income postpartum women with obesity lose weight.
Study Duration:	8-weeks
Subject Duration:	8-weeks

1.2 SCHEDULE OF ACTIVITIES (SOA)

	Enrollment/ Baseline	Weekly during Meal Delivery Intervention	8-weeks (Follow-Up)
Demographics	X		
Pregnancy & Medical History	X		
Intervention Adherence Survey		X	
Diet Satisfaction (Diet Satisfaction Questionnaire; DSAT-28) ¹	X		X
Anthropometrics (weight, height)	X		X
Food Security (18-item US Household Food Security Survey Module)	X		X
Perceived Stress (10-item Perceived Stress Scale; PSS-10) ^{2,3}	X		X
Healthy Eating Self-Efficacy (from Lipsky LM et al. 2016) ⁴	X		X
Weight Control Self-Efficacy (from Lipsky LM et al. 2016) ⁴	X		X

2 INTRODUCTION

2.1 STUDY RATIONALE

Many women fail to return to their pre-pregnancy weight postpartum (i.e., postpartum weight retention, PPWR).⁵⁻¹⁰ PPWR and interpregnancy weight gain are important predictors of long-term obesity risk.¹¹⁻¹³ Despite gaining similar amounts of weight during pregnancy, Black women are more likely to retain and accrue considerable amounts of weight postpartum compared to White women.¹³⁻¹⁶ PPWR and interpregnancy weight gain negatively impact maternal cardiometabolic health and increase risk for adverse outcomes in subsequent pregnancies which are more common among Black women and those of lower socioeconomic status.¹⁷⁻²⁴ Black and lower income women are also disproportionately burdened by obesity,²⁵ which further increases the risk for PPWR, interpregnancy weight gain, and adverse health outcomes.²⁶⁻²⁸ Behavioral interventions to prevent PPWR have had limited success, particularly among women with obesity.²⁹⁻³² Most PPWR interventions involve high participant burden and fail to sufficiently address both the psychological (e.g., low self-efficacy) and material (e.g., food insecurity) barriers and needs of low-income, minority women.³¹⁻³⁶ One promising and novel alternative approach capable of overcoming many of these barriers is the provision of healthy, home-delivered meals. In non-pregnant populations, meal delivery has been used to help manage various conditions including obesity with cost-effective and encouraging results.³⁷⁻⁴³ Importantly, meal delivery for postpartum weight management may be sustainable given the cost-savings demonstrated in other populations and the recent expansion by public and private insurers to cover home-delivered meals.^{41,42,44-46} Despite demonstrated success for managing other medical conditions, meal delivery for managing postpartum weight has not been studied.^{37-43,47} Thus, the purpose of the proposed pilot study is to assess the feasibility and acceptability of a meal delivery intervention for postpartum weight loss among predominantly Black and low-income postpartum women with obesity using a single-group design. Findings from this pilot study will inform future refinements to the intervention which we plan to test and further refine in a future pilot study.

2.2 BACKGROUND

An estimated 60-75% of women fail to return to their pre-pregnancy weight (i.e., postpartum weight retention, PPWR) and up to 60% of women actually gain weight postpartum.⁵⁻¹⁰ PPWR and interpregnancy weight gain are important predictors of long-term obesity risk.¹¹⁻¹³ Women of lower socioeconomic status and from racial/ethnic minority groups are disproportionately affected¹³ and represent “priority populations” (i.e., those deserving priority in public health and clinical efforts).⁴⁸ Despite gaining similar amounts of weight during pregnancy,¹³ Black women are estimated to retain an average of 6.4 pounds more and are twice as likely to retain more than 20 pounds at 1-year postpartum compared to their White counterparts.^{14,15} Additionally, there is evidence of racial/ethnic differences in weight trajectories postpartum. On average, Black and White women lose similar amounts of weight across the first 6 weeks to 3 months postpartum, after which Black women exhibit gains in weight and body mass index (BMI) from 3 to 12 months postpartum while White women continue to lose weight across the first year postpartum.^{49,50} Women with lower levels of education and those of lower income have also been shown to be an increased risk of PPWR.^{5,7} This is extremely concerning, as excess weight retention or weight gain following pregnancy may be particularly harmful, given evidence of preferential central fat deposition postpartum.⁵¹⁻⁵³ Visceral adipose tissue, which is associated with several cardiometabolic risk factors,^{54,55} is estimated to increase by 30-45% in the first year postpartum.⁵¹⁻⁵³

PPWR and interpregnancy weight gain can exacerbate these unfavorable changes in body composition and cardiometabolic health, which can have important short- and long-term health implications.^{51,52,56,57} PPWR and interpregnancy weight gain not only alter a woman's future chronic disease trajectory, increasing the risk for new or worsening obesity,^{11,12,58} but also increase risk for adverse outcomes in subsequent pregnancies including hypertensive disorders of pregnancy,¹⁷ preterm delivery,^{18,19} and caesarean birth^{20,59} which are more common among women from priority populations.²¹⁻²⁴ Black and lower income women are also disproportionately burdened by obesity,²⁵ which further increases the risk for PPWR, interpregnancy weight gain, and adverse maternal-child health outcomes.²⁶⁻²⁸ Thus, there is great interest in effective interventions to improve postpartum weight management due to the important health implications for women and children, particularly among priority populations.

Unfortunately, even the most intensive behavioral interventions, which typically focus on caloric restriction, improving diet, and/or increasing physical activity, have had limited success for PPWR, particularly among women with obesity.^{29-32,60} Based on meta-analyses, <2.5-kg weight reductions are observed with postpartum lifestyle intervention compared to standard care.^{29,30,32} Lifestyle interventions for PPWR also show high levels of attrition and poor intervention adherence.^{29-32,60} The postpartum period is important not only for maternal weight management and long-term obesity risk, but also for preparing women for healthy subsequent pregnancies as part of preconception planning. Entering subsequent pregnancies with excess adiposity increases the risk for PPWR,^{10,27} creating a cycle in which women accrue additional weight with each pregnancy, leading to new or worsening obesity.²⁷ Exposure to maternal overweight/obesity in utero, in turn, increases the child's subsequent risk for developing obesity,^{61,62} type 2 diabetes,⁶³⁻⁶⁵ and cardiovascular disease.⁶⁶ Thus, postpartum weight management interventions are needed to promote healthy weight and prevent new or worsening obesity among mothers, as well as to prevent complications in subsequent pregnancies and reduce offspring long-term risk for obesity and chronic diseases.^{26,61,66}

Most postpartum weight management interventions are intensive, comprehensive, and involve high participant burden by requiring significant effort and psychological and physical resources (e.g., self-regulation, time, financial means, access to healthy foods).^{32,33} Such interventions may not adequately address social determinants of health (SDH; e.g., income, education, race/ethnicity, access to care, residential environment) that contribute to disparities in PPWR and obesity in priority populations.⁶⁷ Most PPWR interventions also fail to address psychological (e.g., stress, low self-efficacy) and material (e.g., food insecurity, transportation) barriers of low-income and minority women.³¹⁻³⁶ Achieving meaningful behavior change may be especially challenging postpartum, as women face additional stressors and barriers including lack of time for cooking/shopping, limited access to healthy food, and lack of basic cooking skills.^{31,34-36,68-70} Women with a higher BMI may have more perceived barriers and lower self-efficacy to healthy behavior change postpartum.⁷⁰ A simplified approach targeting a few key behaviors may be particularly well-suited for under-resourced populations.⁷¹ Also, postpartum weight management strategies are needed that more effectively address insufficient and/or diminished effort and resources, which is particularly relevant for priority populations.

Meal delivery overcomes many barriers common to postpartum weight management interventions that disproportionately burden priority populations. The provision of prepared meals to women's homes offers access to healthy food, thereby providing a physical and financial resource to support healthy eating regardless of income, geographic location, or access to transportation. Meal delivery reduces time and effort involved for meal planning, shopping, and preparation and requires less cognitive and behavioral self-regulation. In addition, pre-portioned meals modify the home food environment, which can support healthy habit formation and improve weight outcomes.^{72,73}

Previous studies in non-postpartum populations demonstrate that meal delivery is an effective tool for managing weight, type 2 diabetes, and cardiovascular disease.³⁷⁻⁴³ However, use of meal delivery to manage PPWR and promote the attainment of a healthy weight postpartum has not been studied. Meal delivery also has additional health benefits that may be particularly impactful postpartum. In non-postpartum priority populations, the provision of home-delivered meals has been shown to improve food insecurity and self-efficacy, reduce stress, and participants report high levels of treatment satisfaction.^{40,74-78} These factors may have important implications for promoting healthy weight loss postpartum. For instance, food insecurity has been associated with PPWR, and this association may be stronger among women with obesity.⁷⁹ There is also evidence that lower self-efficacy for healthy behaviors and weight control may be an important predictor of PPWR,⁴ and women with obesity are more likely to report lower self-belief in their ability to manage their weight postpartum.⁷⁰ Similarly, perceived stress has been shown to predict weight retention following childbirth.⁸⁰ Thus, by potentially improving these constructs, meal delivery may confer additional benefits for postpartum weight management.

The purpose of the proposed pilot study is to assess the feasibility and acceptability of a meal delivery intervention among predominantly Black and low-income postpartum women with obesity using a single-group design. If meal delivery is effective for managing weight postpartum, it may be sustainable given the cost-savings demonstrated in other populations (e.g., individuals with type 2 diabetes, cardiovascular disease).³⁷⁻⁴¹ In 2020, Medicare Advantage expanded to allow coverage of home-delivered meals.⁴⁴ More insurers are piloting meal delivery programs to address SDH for chronic disease management,^{45,46,81-84} with hundreds of contracts between medically-tailored meal providers and health insurance plans nationwide.⁸⁵ A growing number of meal delivery programs are participating in healthcare innovation projects and receiving reimbursement for Medicaid, Medicare, and dually-eligible populations in at least 17 states.^{46,81} Thus, there is the long-term possibility for meal delivery for maternal weight management postpartum to be offered as a covered health care service, thereby providing an accessible community resource and shift in health care policies.

2.3 RISK/BENEFIT ASSESSMENT

2.3.1 KNOWN POTENTIAL RISKS

This study involves providing a healthy meal delivery intervention to promote weight loss among low-income mothers who are 5-45 weeks postpartum. Those with conditions that may put them at increased risk or unique nutritional needs that would make the meal delivery intervention inadvisable will be excluded. Although unlikely, participants may experience normal and temporary physiologic reactions or weight fluctuations associated with healthy dietary changes, such as flatulence (frequency: rare; severity: mild). There is a risk of experiencing an allergic reaction to meals, which is judged to be low as participants self-select meals from provided menus with ingredients. Additionally, participants will be asked to report any food allergies or intolerances at baseline and the PI (who is a registered dietitian) will work with the study's meal delivery partner to accommodate participant food allergies and intolerances, as needed. Participants will also be provided with meal plans designed by the PI (who is a Registered and Licensed Dietitian) in accordance with current micronutrient and macronutrient recommendations for postpartum women. Participants will be instructed to self-weigh at least once per week during the study intervention using a study-provided scale and will be asked to report their weekly weight measurements using a Qualtrics survey sent via email each week of the study intervention.

Concerning weight fluctuations (e.g., weight gain) will be reported to and reviewed by the PI. Concerning weight fluctuations will be investigated and adjustments will be made to meal plans or study procedures, if necessary. Participants will also be closely monitored for any negative effects relating to the meal delivery intervention. Should it be determined that continued participation is contraindicated for a participant, they will be withdrawn from the study. Given that this is a non-invasive meal delivery intervention for postpartum weight management, we do not anticipate that withdrawals will be common. There is a risk of foodborne illness with meal delivery which is judged to be low as we are partnering with an experienced meal delivery company that operates in compliance with local, state, and federal food safety regulations. All meals will be delivered in insulated packaging with frozen gel packs to keep food cold in transit and meal delivery times will be scheduled with participants. In compliance with the Alabama Department of Public Health, home-delivered meals can be safely stored in the refrigerator for 7 days. Thus, fully prepared, refrigerated meals will be delivered once per week to participants' homes. All meals will also come with re-heating instructions. In the unlikely event a participant experiences distress from completing any of the self-report surveys, she will be allowed to skip items or discontinue the assessment. There is a low risk of emotional or psychological discomfort from participants answering personal questions about their health, eating, and activity behaviors.

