3 STUDY DESIGN

3.1 OVERALL DESIGN

This is a single-group intervention trial in which mothers who are 5-45 weeks postpartum and enroll in the trial will receive 10 meals per week for a total of 8-weeks.

Potentially eligible participants will be primarily recruited through the UAB Center for Women's Reproductive Health (CWRH). CWRH nursing staff will prescreen medical records of participants who delivered at UAB. Potentially eligible women will be approached in the postpartum recovery unit following delivery or at their 6-week postpartum appointment by a CWRH research nurse and told about the study. Interested women who meet initial eligibility criteria will be contacted by study staff at 5-45 weeks postpartum to complete a secondary pre-screening via telephone to confirm eligibility. Supplemental recruitment will occur via flyers/ads distributed at UAB obstetrics/gynecological offices, UAB pediatrics clinics, UAB lactation centers, UAB Nurse Family Partnership, local day care centers and churches, local breastfeeding and/or parent support groups, and Birmingham neighborhood associations. Interested women will respond via phone call or email to the public advertisements and be screened by phone.

Interested and eligible women will be scheduled to attend an Enrollment/Baseline Assessment visit during which informed consent will be completed. Those who consent to enroll in the study will then complete baseline study measurements including surveys and anthropometrics.

Within 1-2 weeks of completing the baseline assessment, participants will receive their first study meal delivery order. All participants will receive the study meal delivery intervention for a total of 8-weeks. During the study intervention, participants will be emailed a weekly Qualtrics survey to complete to report intervention adherence.

During the final week of the study meal delivery intervention, participants will complete Follow-up (week 8) assessment visit measurements, including surveys and anthropometrics.

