5 STUDY INTERVENTION

5.1 STUDY INTERVENTION(S) ADMINISTRATION

5.1.1 STUDY INTERVENTION DESCRIPTION

After completing baseline data collection, all participants will receive 10 fully prepared lunch/dinner-style meals per week for a total of 8 weeks. Prior studies indicate that providing 10 meals or meal replacements per week is effective for weight management.^{43,86} We are partnering with a local company, Nourish Foods, to prepare and deliver study meals. Participants will select the 10 meals that they want each week from a weekly rotating menu that includes nutrition and ingredient information to accommodate participants with food aversions or allergies. Participants place meal orders weekly with study staff who will submit orders to the meal delivery partner. During these weekly contacts, trained staff also provide brief behavioral support, including evidence-based strategies of problem-solving, action-planning, and principles of motivational interviewing to help participants identify and navigate adherence barriers.⁸⁷⁻⁹¹ Staff will document the duration and topics discussed. Each week of the intervention, participants will be automatically sent an electronic survey to report the number of study-provided meals consumed by participants (versus others in the household versus thrown out), as we understand meals may be shared in food insecure households. The study coordinator will be available when collecting weekly meal orders to help participants navigate these challenges in multi-member households. If a participant does not place their weekly order, study staff will select meals based on participant preferences and allergies collected at baseline. Meals will be delivered once per week to participants' homes, which is in compliance with the Alabama Department of Public Health guidelines.

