6 STUDY INTERVENTION DISCONTINUATION AND SUBJECT DISCONTINUATION/WITHDRAWAL

6.1 DISCONTINUATION OF STUDY INTERVENTION

Participants will continue to receive the study intervention for the 8-weeks study. The study intervention may be discontinued for a participant if a clinical adverse event (AE) or other medical condition or situation occurs such that continued participation in the study intervention would not be in the best interest of the subject.

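### Section 2.3.1 withdraws a woman from the whole study when continued participation is contraindicated; stopping the meals and keeping her enrolled would save her week 8 data and avoid counting a willing attender as attrition

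*Combined protocol and SAP*

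**What the plan says.** Section 2.3.1 first promises safety monitoring: "Participants will also be closely monitored for any negative effects relating to the meal delivery intervention". The next sentence gives the consequence: "Should it be determined that continued participation is contraindicated for a participant, they will be withdrawn from the study". The wording is mandatory and the consequence is loss of the study, not only of the meals. The same section expects this to be rare ("we do not anticipate that withdrawals will be common").

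Two other sections deal with the same situation in permissive terms. Section 6.1 lets the intervention be stopped when an adverse event or medical condition arises "such that continued participation in the study intervention would not be in the best interest of the subject". Section 6.2 lets the investigator withdraw a woman from the study for much the same kind of event, and says that women withdrawn after receiving the intervention are not replaced.

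Section 3.1 places the last assessment at the end of the meals: "During the final week of the study meal delivery intervention, participants will complete Follow-up (week 8) assessment visit measurements". Section 7.1 says that every study participant has two in-person assessments, baseline and week 8, and the schedule in 1.2 labels the last column as the 8-week follow-up. Section 8.1 sets a target of less than 20% attrition and expects diet satisfaction to improve from baseline to follow-up. Section 8.3.3 defines retention as the share of enrolled women who complete follow-up.

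**The concern.** The hazard described in 2.3.1 comes mainly from the meals, and stopping the meals removes it. Withdrawal from the study adds no protection unless the visit or questionnaires are themselves harmful, and it has two costs.

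First, a woman willing to attend week 8 becomes an attrition case because of the rule and not by her own choice. The attrition result then mixes women who left with women who were removed.

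Second, her week 8 information is lost: the follow-up DSAT-28, FORM 14 (Program Satisfaction, listed only at follow-up) and the interview. The rationale in 2.1 says: "Findings from this pilot study will inform future refinements to the intervention". A woman who had to stop for a medical reason is well placed to say what should be refined.

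**Working it through.** **Which rule applies.** Take a woman whose meals are contraindicated but who is willing to be assessed.

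- Under 2.3.1 read literally, she is withdrawn, has no week 8 visit, and counts as not retained under 8.3.3.
- Under 6.1, her meals stop. If she is not withdrawn she is still a study participant, so the two-assessment requirement in 7.1 covers her, and she counts as retained if she attends.

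The same woman gets a different attrition status depending on which section staff follow.

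**Size of one case.** The plan has no power calculation or loss rate to reproduce. Inputs: N = 11 (1.1 and 7.1) and attrition below 20% (8.1).

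- 1/11 = 9.1%; 2/11 = 18.2% (target met); 3/11 = 27.3% (target missed).
- One rule-driven withdrawal uses one of the two tolerated losses. With two ordinary drop-outs as well, the result is 27.3% if she is withdrawn and 18.2% if she attends.

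**If one such case occurs.** Let q be the loss rate for other reasons (assumed). If she is withdrawn, at most one of the other 10 may be lost: P(Binomial(10, q) ≤ 1). If she is invited and has the same risk as the others: P(Binomial(11, q) ≤ 2).

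| q | Target met, she is withdrawn | Target met, she is invited |
|---|---|---|
| 5% | 91.4% | 98.5% |
| 10% | 73.6% | 91.0% |
| 15% | 54.4% | 77.9% |
| 20% | 37.6% | 61.7% |

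This table is conditional on a case and says nothing about how likely one is.

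**Allowing for how rare cases may be.** Let c be the contraindication rate per woman, a the ordinary loss rate, and t the share of affected women who would attend week 8. All three are assumptions. The expected number affected is 11c = 0.22, 0.55 and 1.1 for c = 2%, 5% and 10%. The rule turns a met target into a missed one when unavoidable losses (rate a + c(1−t)) number at most two, but all losses, including avoidable ones (rate ct), number three or more. The trinomial probabilities for 11 women are:

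| a | t | c = 2% | c = 5% | c = 10% |
|---|---|---|---|---|
| 5% | 1 | 2.2% | 7.4% | 20.6% |
| 10% | 1 | 4.7% | 13.2% | 29.3% |
| 5% | 0.5 | 1.2% | 4.6% | 13.2% |
| 10% | 0.5 | 2.5% | about 7% | 16.1% |

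Contraindications alone would break the target, P(Binomial(11, c) ≥ 3), with probability 0.1%, 1.5% and 9.0%. All these figures also assume that 2.3.1 is always followed literally and 6.1 is never used instead.

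**DSAT-28.** If one woman differs from the rest by 1 SD (assumed), leaving her out moves the mean by 1/11 = 0.09 SD, against a standard error of 1/√11 = 0.30 SD.

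**What is untouched.** The weekly surveys in 7.1 record meals eaten, adverse events and satisfaction with the meals up to exit. The primary adherence endpoint in 8.3.2 is built from completed weekly surveys, so it is not affected.

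**The case against.** The strongest case against is that the plan largely handles this already. Section 6.1 separates stopping the intervention from leaving the study, and 6.2 makes withdrawal discretionary. A sensible investigator could stop the meals and keep the woman. This stands, and it limits the point. It does not remove it, because 2.3.1 still gives a mandatory instruction that disagrees with both sections.

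A reader might go further and infer from the placing of the week 8 visit in the last week of meals that a woman off the meals has no visit to attend. The documents do not support that. The requirement in 7.1 covers all study participants and does not depend on receiving meals, and the schedule is labelled by week. The last week of meals is most naturally read as a calendar position.

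The 2.3.1 trigger can also be read like 6.2, as covering women for whom the study itself is unsuitable. That reading is possible. But the preceding sentence is about negative effects of the meals, so the text is at best ambiguous.

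A reader might also infer a serious loss of acceptability data. That is too strong. Weekly satisfaction data remain, FORM 14 and the interview enter no planned analysis, and a DSAT-28 completed off the meals describes a different diet. Nor does the rule reach women who merely dislike certain meals ("Participants will select the 10 meals that they want each week from a weekly rotating menu") or whose weight change is a concern ("adjustments will be made to meal plans or study procedures, if necessary").

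Finally, a woman medically unable to continue is a genuine feasibility signal, and counting her as retained could hide it. This also stands, and the reporting has to show it.

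**Conclusion.** The point holds as a minor one. Read literally, 2.3.1 produces a worse result than 6.1 with no gain in safety. A willing attender becomes attrition at 9.1 points per woman, and her week 8 DSAT-28, FORM 14 and interview are lost. Among the planned results, only attrition and, slightly, the DSAT-28 means can change.

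The per-woman arithmetic follows from the documents. Every probability rests on assumed rates: the plan gives no contraindication or drop-out rate, and the higher figures need contraindication to be more common than the plan's own expectation suggests. The analysis is descriptive, and no stated decision depends on the attrition target.

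**What to change.** - **Section 2.3.1:** state that when the meals are contraindicated they are stopped under 6.1, and that the woman stays enrolled and is invited to the week 8 visit unless she withdraws consent or the assessments themselves are contraindicated.
- **Section 6.2:** for medical contraindications, reserve withdrawal from the study for those two cases. The non-compliance reason in 6.2 is a separate matter.
- **CONSORT diagram (8.3.3):** show women who stopped meals, with reasons, separately from women who did not complete follow-up, and print that count beside the attrition result. Keep the retention definition as it is.
- **DSAT-28 (8.3.3):** flag follow-up scores from women off the meals and give the means with and without them.

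**Cost:** a sentence or two in the protocol, one line in the diagram, and a second set of means if any woman is affected. The visit, forms and gift card are already planned for every woman, and safety is unchanged because the meals still stop. There are two downsides: an off-meal DSAT-28 does not reflect the intervention, and a woman who stopped meals early can count as retained. The separate line and the paired means make both visible. If enrolment is already complete, the two reporting changes remain available wherever the data allow.
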